2.3 Rationale for the methodology

The methodology retained for this efficacy (phase II) study is a randomized trial, which is the design presenting the highest level of evidence.

We started to assess parameters by comparing data collected at 3 visits:

- Visit 1: inclusion, data collected for 6 weeks before treatment and during the visit
- Visit 2: end of treatment, data collected during the 6 weeks preceding the visit (i.e. 6 weeks of treatment) and during the visit
- Visit 3: end of study, data collected during the 6 weeks preceding the visit (i.e. 6 weeks following the end of treatment) and during the visit.
- In addition, data are collected on pharmacokinetic at Day 8 and Day 22 (blood sample) and on safety at Day 15 and Day 31 (phone call).

[figure not shown]

Figure 4 General diagram of the study

For safety reasons, as no tolerance data are available with a nasal administration, we decided to include patients sequentially. We designed an inclusion scheme in 3 or 4 steps. An independent safety committee will give its recommendations on the continuation of the study.

The theoretical inclusion scheme is described as follows. It was established pragmatically based on our sample size.

We consider that a cessation of treatment for at least 8 consecutive days, for safety concern, that is to say adverse reaction due to the ointment, is a major issue.

- **STEP 1- 8 patients will be included in Lyon.**

On day 31 (phone call): information regarding adverse events (AE), severe adverse events (SAE) and observance of the treatment for the first 30 days of treatment are collected for these 8 patients.

Based on these data, a DSMB meeting (#1) will be consulted and will give its recommendations on the continuation of the study according to the following theoretical scheme:

Number of patient who stop treatment for 8 consecutive days		ARM PLACEBO				
		0	1	2	3	4
ARM ACTIV	0	0	1	2	3	4
	1	1	2	3	4	5
	2	2	3	4	5	6
	3	3	4	5	6	7
	4	4	5	6	7	8

The numbers inside the table = total number of events in both arms

	No imbalance between arms
	Imbalance between arms active>placebo
	Imbalance between arms placebo>active
	+ 16 patients
	+ 8 patients
	Stop

If there is no imbalance between arms (difference ≤ 1), the total number of patient who stop treatment at least 8 consecutive days will be consider (semi-blind data transmitted to DSMB):

- < 4 patients in both arms \rightarrow inclusion of 16 new patients (Step 2A)

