6.2.2 Recommendations

Patients will receive recommendations on how to contact the doctor in case of the onset of adverse events.

A burning sensation is frequently observed at the administration site; usually this sensation is acceptable and disappears after a few days of administration.

In case of an adverse event probably due to the product: skin irritation, an unacceptable burning sensation, pruritus, and erythema, at the application site:

- The patient must stop the treatment.
- He or she must inform the investigator as soon as possible.
- Based on symptoms, a medical consultation can be carried out by a general practitioner, a specialist or an investigator involved in the study.
- The treatment can be reintroduced, or not, after clinical normalization.
- It is up to the investigator to make the decision in the interest of the patient, on the basis of the balance between the risk of a new event and the risk of aggravation of the disease.

The modalities for managing nosebleeds will be given to the patients to inform all doctors of the treatment of the nosebleeds specific to this disease.

6.3 Phone calls on day 15, 14 days after the beginning of the treatment (up to day 18 tolerated)

Patients will be contacted by phone, 14 days after the beginning of the treatment, to collect intermediate data regarding tolerance and observance.

The following data will be collected:

- Treatment observance: any interruption to the treatment interruption will be noted precisely (date, duration), as will the reason for the interruption.
- Occurrence of adverse events: nature, date of onset, and whether or not a symptomatic treatment was given.
- Any change in the concomitant treatments.
- The date of the blood sample planned at day 8 (FK506 dosage).

6.4 Phone calls on day 31, 30 days after the beginning of the treatment (up to day 37 tolerated)

Patients will be contacted by phone, 30 days after the beginning of the treatment, to collect intermediate data regarding tolerance and observance.

The following data will be collected:

- Treatment observance: any interruption to the treatment interruption will be noted precisely (date, duration), as will the reason for the interruption.
- Occurrence of adverse events: nature, date of onset, and whether or not a symptomatic treatment was given.
- Any change in the concomitant treatments.
- The date of the blood sample planned at day 22 (FK506 dosage).

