6.5 Visit at the end of the treatment, V2 = at day 43 (up to day 50 tolerated)

The patients will be seen in consultation, in the Reference center or skill center for HHT.

The following examinations/consultations will take place:

- Clinical examination including blood pressure and heart rate.
- Collection of the nosebleed grids completed by the patients during the 6 weeks of treatment (Appendix 1: Nosebleed monitoring grid), if not completed on line. These grids include monitoring of treatment administrations.
- The ESS questionnaire is completed by patient (Appendix 2).
- New nosebleed grids will be given to the patients for ENT monitoring during the next 6 weeks (Appendix 1: Nosebleed monitoring grid), if not completed online.
- The number of red blood cell transfusions received by the patient in the last 6 weeks will be noted.
- Patients will return the product, it will be transmitted to the hospital pharmacy.
- A set of biological blood samples (2 x 5 mL tubes) is collected: hemoglobinemia and serum ferritin.
- A blood sample is collected (4 mL on EDTA) for tacrolimus dosage.
- An SF36 quality of life questionnaire will be given to patients for completion.
- Monitoring and collection of any adverse events.
- Concomitant treatments will be noted.

6.6 Visit after 6 weeks follow-up, V3 = at day 85 (up to day 100 tolerated)

The patients will be seen in consultation, in the Reference center or skill center for HHT.

The following examinations/consultations will take place:

- Clinical examination including blood pressure and heart rate.
- Collection of the nosebleed grids completed by the patients during the 6 weeks' follow-up after the treatment (Appendix 1: Nosebleed monitoring grid), if not completed online.
- The ESS questionnaire is completed by the patient (Appendix 2).
- The number of red blood cell transfusions received by the patient in the last 6 weeks will be noted (as noted by the patient on the nosebleed grids).
- A set of biological blood samples (2 x 5 mL tubes) is collected: hemoglobinemia and serum ferritin.
- An SF36 quality of life questionnaire will be given to patients for completion.
- Monitoring and collection of any adverse events.

- Concomitant treatments will be noted.

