7.4 Specific management of complications

7.4.1 Nosebleeds

Patients will have access to the standard management techniques for nosebleeds in HHT. ENT monitoring will be ensured before the start of administration, after 6 weeks of treatment and 6 weeks after the end of the treatment so as to note any modification to the nasal mucosa during the treatment (Appendix 3: ENT monitoring examination). The modalities for the management of nosebleeds will be given to the patients, as described in the "PNDS" (Protocole National de Diagnostic et de Soin), so that they may inform any doctor of the treatment modalities for the nosebleeds specific to this

pathology. Emergency document (see Appendix 4), accessible on the internet http://www.favamulti.fr/wp-content/uploads/2016/05/37_RO-Epistaxis.pdf, is given to the patients.

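### DSMB meeting #1 is not scheduled to see nosebleed durations, so increased bleeding counts only if it is reported as an AE/SAE or leads to a treatment stop of at least 8 days

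*Combined protocol and SAP*

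**What the plan says.** Section 2.3 includes patients in steps because there are no tolerance data for the nasal route. The first step is stated as "STEP 1- 8 patients will be included in Lyon". At the day-31 call, "information regarding adverse events (AE), severe adverse events (SAE) and observance of the treatment for the first 30 days of treatment are collected". The DSMB then "will give its recommendations on the continuation of the study according to the following theoretical scheme".

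The event counted in that scheme is "a cessation of treatment for at least 8 consecutive days, for safety concern, that is to say adverse reaction due to the ointment". If the arms differ by at most one stop, the DSMB receives semi-blind data; unblinded data follow only when the difference exceeds one. Meeting #2 (Step 2A or 2B) adds a safety assessment of the end-of-treatment visit for the first 8 patients. Its threshold is a total across both arms, for example fewer than 12 stops among 24 patients.

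Section 6.4 sets the content of the day-31 call: observance, concomitant treatments, a blood-sample date and "Occurrence of adverse events: nature, date of onset, and whether or not a symptomatic treatment was given". Section 6.2.2 tells patients when to stop: "In case of an adverse event probably due to the product: skin irritation, an unacceptable burning sensation, pruritus, and erythema, at the application site". Bleeding is not in that list.

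Nosebleeds are recorded daily (6.1), and a completed 6-week baseline is required for inclusion (4.2.5). At V2, section 6.5 provides for "Collection of the nosebleed grids completed by the patients during the 6 weeks of treatment", unless they were entered online. Section 7.4.1 schedules ENT monitoring before treatment, after 6 weeks of it and 6 weeks later, "so as to note any modification to the nasal mucosa during the treatment".

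**The concern.** The stepwise scheme exists to protect patients on an untested route. The trial holds a daily local measurement with a 6-week baseline in every patient, yet the committee that advises on opening enrolment is not scheduled to see it.

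These patients bleed habitually. Whether heavier bleeding becomes an adverse event at a phone call depends on the patient and the investigator judging it beyond the usual disease, and the protocol does not say when that is so. Section 7.2.2 also ends AE recording after disease progression, a term it does not define for HHT. A rise in bleeding that is neither reported nor followed by a long stop would leave the count at 0 v 0. The next 16 inclusions would then open, on semi-blind data, without the recorded durations having been looked at.

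**Working it through.** **Plan's own figure.** The plan gives none for this point. Its sample size (22 per group, 60% v 15%) reproduces, with an exact Fisher power of 82.7%, and plays no part here.

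**Timing.** The meeting #1 data are cut at the day-31 call (tolerated to day 37). Paper grids come in at V2, day 43 (tolerated to day 50), nominally 43 − 31 = 12 days later. Online entry (4.3.2, 6.2) is optional and would put some patients' grids in hand earlier. Table 1 marks grid surrender at the two calls but grid collection only at V1, V2 and V3, so it does not show that completed grids reach the team by day 31.

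**How the step rule responds to bleeding.** Inputs from 2.3: 8 patients and a decision table running from 0 to 4 stops per arm. Assumptions: a 4:4 split, and no placebo stops. The rule then reads:

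- 0 or 1 active stops: 16 new inclusions
- 2 active stops: 8 new inclusions
- 3 or 4 active stops: inclusions may be discontinued

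Let every active patient bleed more, and let s be the chance that this leads to a stop of at least 8 days attributed to the ointment. Active stops are then Binomial(4, s). For s = 0.25:

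- P(16 more) = 0.75⁴ + 4 × 0.25 × 0.75³ = 0.316 + 0.422 = 0.738
- P(8 more) = 6 × 0.25² × 0.75² = 0.211
- P(may be discontinued) = 1 − 0.738 − 0.211 = 0.051

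| s | 16 more | 8 more | may be discontinued |
|---|---|---|---|
| 0 | 100% | 0% | 0% |
| 25% | 73.8% | 21.1% | 5.1% |
| 50% | 31.25% | 37.5% | 31.25% |
| 100% | 0% | 0% | 100% |

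With a 10% background stop rate in both arms and s = 0, the first column is 96.2%. The rule sees bleeding only through stops, and its response depends almost wholly on s, for which the documents give no value.

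**The 4:4 split.** Section 4.4 gives no block size. Under simple randomisation an exact 4:4 split has probability 70/256 = 27%.

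**What the durations could show at this size.** If bleeding worsened in 4 of 4 active and 0 of 4 placebo patients, the two-sided Fisher p is 2/70 = 0.029. For 3 of 4 v 0 of 4 it is 0.143. Only the most extreme pattern passes 5%, so the table would inform clinical reading rather than a test.

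**The case against.** A reader might infer that increased bleeding cannot influence the first step decision. The documents do not support that:

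- Section 7.1.1 defines an adverse event as any untoward occurrence and does not exclude epistaxis. A bleed needing hospitalisation is an SAE (7.1.2).
- Section 4.3.2 names the epistaxis grids among the sources for AEs and SAEs. Patients are asked about adverse events at two calls, and the Appendix 1 grid has space for important events.
- The counted stop is any adverse reaction due to the ointment, not only those listed in 6.2.2. A stop attributed to ointment-related bleeding would count.
- The scheme is called theoretical and the DSMB gives recommendations, so 0 v 0 stops does not bind it.

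A reader might also infer that bleeding is left out of every step up to 48 patients. That goes too far as well. The full on-treatment grids of the first 8 patients arrive at V2, and meeting #2 includes a safety assessment of that visit's data. The text neither specifies nor excludes a comparison of bleeding by arm. Nor do the documents identify bleeding as the main local harm; section 11.2 expects burning or irritation, and nothing shows that bleeding is under-reported at calls.

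All of this stands, and it limits the point to insensitivity. It does not supply what is missing: recorded durations, set against baseline, in front of the committee at its first decision.

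Two objections bear on the fix. By-arm tables in every report would override the plan's semi-blind handling; coded group labels meet that. On-treatment duration is also a secondary efficacy criterion, so the DSMB would see interim efficacy-type data. That is a real cost, though it is not the primary post-treatment window.

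**Conclusion.** The point holds in a limited form. Meeting #1 is not scheduled to receive nosebleed durations. The numerical rule reacts to more bleeding only through stops of at least 8 days, and the committee otherwise learns of it only through reported AEs or SAEs. For patients on paper grids, the daily record is not in hand at the day-31 cut. Meeting #2 adds V2 data for the first 8 patients without specifying a comparison of bleeding between arms.

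The size can only be illustrated: when all active patients worsen, the probability of opening 16 inclusions runs from 100% to 0% as the chance of a long stop runs from 0 to 1. This rests on an assumed 4:4 split, no other stops and assumed stop rates. The primary analysis and the sample size are unaffected. This is a cheap improvement to the DSMB report, not a flaw that invalidates the scheme.

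**What to change.** In 2.3 and 12.2, add one per-patient table to each DSMB report:

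- Total nosebleed minutes and red-cell units over the first 30 days of treatment, beside the patient's own baseline scaled to 30 days (42-day total × 30/42 = 0.714 × total).
- Full 6-week values for patients past V2.
- Arms shown as coded groups A and B whenever the plan calls for semi-blind data.

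Take the values from online grids, or have paper users read out or send their grid totals at the existing day-31 call. State that the table serves harm review only, with no numerical threshold and no efficacy stopping; no alpha is then spent. It would also help to say in section 7 when increased epistaxis is to be recorded as an AE.

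The cost is extra time at the call for paper users, who may have up to 30 daily totals to report, and one more table. The independent DSMB would also see on-treatment bleeding by coded arm during the trial.

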- ≥ 4 patients in both arms \rightarrow inclusion of 8 new patients (Step 2B)

Note: if a large number of patients stopped the treatment for at least 8 consecutive days, the hypothesis will be that the ointment form is not well accepted. Then we consider it is worthwhile to check this point by including 8 additionnal patients.

If there is an imbalance between arms (difference > 1), (unblinded data will be transmitted to DSMB):

- The number of “stops” is higher in the placebo arm
 - If “0” or “1” patients in active arm stop treatment \rightarrow inclusion of 16 new patients (**Step 2A**)
 - If “2” patients in active arm stop treatment \rightarrow inclusion of 8 new patients (**Step 2B**)
- The number of “stops” is higher in the active arm
 - If difference between arms is 2 \rightarrow inclusion of 8 new patients (**Step 2B**)
 - If difference between arms is over 2 \rightarrow inclusions may be discontinued (**Step 2C**).

The first 8 patients will be included in the Lyon center. Further inclusions will take place in all centers.

For the following steps, we consider the total number of patients who have a cessation of treatment for at least 8 consecutive days for safety concerns. Indeed, if 50% or more of patients are “in failure”, the continuation of the study may be called into question and the analysis on the main judgement criteria will then not be relevant.

- **STEP2 – Following inclusions, all centers**

STEP 2A- In case of inclusion of 16 new patients.

For these 16 patients, on day 31 (phone call): information regarding adverse events (AE), severe adverse events (SAE) and observance of the treatment for the first 30 days of treatment are collected. Additionally, safety assessment is carried out on the data collected at the visit after the end of treatment for the first 8 patients.

Based on these data, a DSMB meeting (#2) will be consulted and will give its recommendations on the continuation of the study according to the following theoretical equations:

- If less than 12 of the 24 patients stop treatment for 8 consecutive days due to safety concerns, 24 new patients will be included (**Step 3A**). Total number of patients included: $8 + 16 + 24 = 48$.
- If 12 or more patients stop treatment for at least 8 consecutive days due to safety concerns, depending on the group imbalance, the DSMB may request the lifting of the blind and inclusions may be discontinued (**Step 3B**). Total number of patients included: $8 + 16 = 24$.

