4.4 Randomization, blinding and lifting the blind

The randomization process will be centralized. Allocation of a randomization arm to a patient included will be made by IWRS (Interactive Web Response System), on the basis of a unique randomization list for all investigation centers.

The lists of randomization will be pre-established, by the “Pole IMER” at the Hospices Civils de Lyon – Clinical Research Unit.

Clinsight (Ennov clinical) software will be used to manage this study.

During the inclusion visit, after verifying the inclusion criteria, the investigator connects to the platform to include the patients in the eCRF. This will assign an identification number. When inclusion is validated, the patient is randomized and a treatment code is allocated by the system. The treatment is then dispensed by the pharmacy at the Hospital Center.

This will be a double blind study in which neither the patient nor the investigator will be aware of the nature of the treatment administered so as to annul any bias in the follow-up and measurements.

Tubes of Tacrolimus 0.1% or placebo will be identical and will have appropriate labeling.

Should a serious adverse event occur, the main investigator, the co-investigators or the sponsor may request that the Anti-Poison Center in Lyon lift the blind 24h/24h (the phone number is written on the clinical trial participation card). The written detailed procedures for lifting the blind will be given to the investigators and the Anti-Poison Center in Lyon.

All requests for unblinding must be justified. Most often, study drug discontinuation and knowledge of the possible treatment assignments are enough to treat a study patient who presents with an emergency condition. When the investigator asks for unblinding, he/she must provide patient identifying information, the date, and the reason for unblinding. The investigator will be informed of the details of the drug treatment.

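### The printed Step 1 rule could let Lyon staff infer that both stoppers are on tacrolimus if two stops are followed by a cohort of 8

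*Combined protocol and SAP*

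**What the plan says.** Section 2.3 describes sequential inclusion. In Step 1, "8 patients will be included in Lyon". The event counted is "cessation of treatment for at least 8 consecutive days, for safety concern". After the day 31 calls the DSMB makes a recommendation under a scheme that the text calls theoretical. The scheme is written out by arm:

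- Arms differ by at most 1: 16 new patients if total stops are below 4, and 8 if they are 4 or more.
- Placebo exceeds active by more than 1: 16 new patients if 0 or 1 active patients stopped, and 8 if 2 did.
- Active exceeds placebo: "If difference between arms is 2", 8 new patients; if it is larger, inclusions may be discontinued.

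On blinding, section 4.4 says that "neither the patient nor the investigator will be aware of the nature of the treatment administered". On what the site knows, section 6.2.2 says of a patient who stops for a local reaction: "He or she must inform the investigator as soon as possible". At the day 15 and day 31 calls (sections 6.3 and 6.4), "any interruption to the treatment interruption will be noted precisely (date, duration), as will the reason for the interruption". Under section 11.8 the main investigator signs a copy of the final protocol.

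Section 2.3 calls data semi-blind or unblinded only in relation to what the DSMB receives. Section 12.2 says that recommendations go to the ANSM. No section keeps the rule in a closed document or says what sites are told after a meeting.

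**The concern.** A decision rule that depends on the split between arms carries information about that split. It does no harm if those who see the decision do not know the rule, or do not know who had the event. Here Lyon staff can know both. They know which of their 8 patients stopped, and the rule is in a document that they hold. If they also learn how many patients are to be enrolled next, they can read the rule backwards.

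The same staff judge causality and intensity of adverse events, decide whether ointment is reintroduced, and manage nosebleeds. Under section 9.2.2.6, nasal surgery or a substitute treatment makes a patient a failure on the primary criterion, so care decisions can also reach the endpoint.

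**Working it through.** The plan gives no probability for any Step 1 result, so there is no figure to reproduce. The check has three parts.

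**1. Reading the rule backwards.** Input: the branch rules in the text of section 2.3. The cell shading and the inclusion flow chart are not readable in the text available, so the map rests on the wording. Entries are the next step for each pair of stop counts.

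| Active stops | Placebo 0 | 1 | 2 | 3 | 4 |
|---|---|---|---|---|---|
| 0 | +16 | +16 | +16 | +16 | +16 |
| 1 | +16 | +16 | +16 | +16 | +16 |
| 2 | **+8** | +16 | +8 | +8 | +8 |
| 3 | halt | +8 | +8 | +8 | +8 |
| 4 | halt | halt | +8 | +8 | +8 |

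Group the cells by what staff could see: total stops and next step. Splits are written active-placebo. The chance that a given stopper is on active weights each split (a, p) by C(4,a) × C(4,p), that is, 4 per arm and no prior difference in stop rates. With no information it is 0.50.

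| Total stops, next step | Possible splits | Chance a stopper is active |
|---|---|---|
| 2, +8 | 2-0 only | 1.00 |
| 2, +16 | 0-2, 1-1 | 16/(22 × 2) = 0.36 |
| 3, +16 | 0-3, 1-2, 2-1 | 72/(52 × 3) = 0.46 |
| 3, halt | 3-0 only | 1.00 |
| 4, +16 | 0-4, 1-3 | 16/(17 × 4) = 0.24 |
| 4, +8 | 2-2, 3-1 | 120/(52 × 4) = 0.58 |
| 4, halt | 4-0 only | 1.00 |
| 5, +16 | 1-4 only | 0.20 |
| 5, +8 | 2-3, 3-2 | 0.50 |
| 5, halt | 4-1 only | 0.80 |
| 1, 6, 7 or 8 | no arm information | 0.50 |

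Among results seen through a cohort size, only two stops followed by 8 fixes every stopper's arm. That deduction does not need a 4:4 allocation. Statements about non-stoppers do. The 0-to-4 table implies 4:4, but section 4.4 gives no block size.

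**2. How likely the 2-0 split is.** The stop rates are assumptions: q on active, r on placebo, independent binomials with 4 per arm.

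P(2-0) = 6q²(1 − q)² × (1 − r)⁴. With r = 5%, (0.95)⁴ = 0.8145.

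| q | 6q²(1 − q)² | P(2-0) |
|---|---|---|
| 5% | 0.0135 | 1.1% |
| 10% | 0.0486 | 4.0% |
| 20% | 0.1536 | 12.5% |
| 30% | 0.2646 | 21.6% |
| 40% | 0.3456 | 28.1% |

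With equal rates of 10%, 20% or 30% in both arms it is 3.2%, 6.3% or 6.4%.

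**3. Timing.** Meeting 1 needs the day 31 call (tolerated to day 37) for all 8 patients. V2 is at day 43. If the meeting follows promptly, the post-treatment window (days 43 to 84) of the latest patients has not yet opened. Their last visit, at day 85, is then 85 − 37 = 48 to 85 − 31 = 54 days away, or up to 100 − 31 = 69 days with the tolerated window.

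**The case against.** Several points on the other side stand. The scheme is advisory and the DSMB also sees adverse events, so it may depart from the table; the inference is exact only if it does not. No passage says that sites are told the next cohort size. All centres enrol after Step 1, so Lyon might learn it only when inclusion pauses. At 48 patients in 18 months, 8 patients take on average 8 ÷ (48/18) = 3 months, probably after first-cohort follow-up has ended. The documents are silent here: they establish neither disclosure nor masking.

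The higher stop rates may also be pessimistic. Section 2.2 expects burning to be transient and usually not to interrupt treatment, which points to the lower rows of the probability table. Little of the 42-day treatment remains after meeting 1. The primary outcome comes from grids that patients complete daily, and nothing suggests that patients learn the stop count or cohort size.

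A reader might infer that the double blind fails for the whole first cohort, or that any stop count with its decision reveals the arms. The enumeration does not support this: most results only shift the odds, and some carry no information. Nor should halts be added to the probability. With r = 5% and q of 20, 30 or 40%, counting them raises the chance that the split is fully revealed to 15%, 29% or 43%, but a halt cannot be hidden by any wording. Five stops followed by 16 fixes the split but not which stopper is on active. At those rates its probability is 4q(1 − q)³ × 0.05⁴, about 2 to 3 in a million.

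What remains is the single 2-0 route, with no safeguard described against it.

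**Conclusion.** The point holds in this limited form. If the DSMB follows the printed scheme and Lyon staff learn the size of the next cohort, two stops followed by 8 more patients tell them that both stoppers are on tacrolimus. This could happen before the primary window of the latest patients opens. The chance runs from about 1% to 28% over the assumed active stop rates of 5% to 40% with 5% on placebo. It is highest when tacrolimus is the less well tolerated arm, which is the situation the rule is meant to detect.

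Direct reach is 2 of 48 patients (4.2%), unmasked to staff and not to patients. The effect on the primary comparison is therefore probably small. Causality assessment, adverse event grading and care decisions for those patients are more exposed. This is a cheap improvement to the plan, not a flaw that threatens its conclusion.

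**What to change.** Keep the sequential scheme and every threshold as they are, and change where the rule is kept and what sites are told:

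- Move the Step 1 arm-by-arm table and branch rules from section 2.3 to a confidential DSMB annex or charter. Submit it to the CPP and ANSM so that the safety rules remain reviewable, and withhold it from site investigators.
- State in sections 2.3 and 12.2 that sites are told only to continue, pause or stop, and name who receives the full recommendation. The main investigator chairs the Scientific Committee (section 12.1), so that committee should not be the recipient.
- Have the IWRS release the next places in a lot of 8 in either branch, so that the first release looks the same.

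The cost is an amendment under section 11.6 and an IWRS setting; sample size and analysis do not change. Sites lose advance sight of the rule and of the next cohort size. The lot of 8 delays the signal and does not remove it: a later pause may still show which branch was taken, though probably after most or all first-cohort patients have completed follow-up. Investigators who have already read the rule cannot unlearn it, so for them the protection comes from the uniform message and the equal first lot.
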